### **2.3 Patient disposition, demographics and other baseline characteristics**

Demographic and other baseline data (including disease characteristics) will be summarized descriptively by treatment group for the FAS.

Categorical data will be presented as frequencies and percentages. For continuous data, mean, standard deviation, median, 25th and 75th percentiles, minimum, and maximum will be presented.

Demographic characteristics to be summarized: age, sex, race, ethnicity, weight, height, BMI, and ECOG performance status.

Disease characteristics: type of MF, baseline spleen size and volume, MF-7 score, prior MF treatment, JAK2 mutation status, CALR mutation status, MPL mutation status, HMR mutation status, number of individual mutations, baseline hemoglobin level (as continuous variable and relative to 10g/dL), platelet count (as continuous variable and relative to 75,000/ $\mu$ L), absolute neutrophil count (ANC) (continuous variable and relative to 1000/ $\mu$ L), white blood count (continuous variable and relative to  $WBC > 15 \times 10^3 / \mu L$ ).

#### **2.3.1 Patient disposition**

The number of patients who had molecular pre-screening, number of screened patients and number of patients randomized will be tabulated. This summary will be produced for all pre-screened patients. Reasons for screening failure will be summarized and listed.

Patient disposition will be tabulated for the treatment period 1. FAS will be used for these summaries. The summary will include the number of patients who were randomized, treated, ongoing, permanently discontinued from treatment period 1 and went to treatment period 2. Patient disposition for both treatment period 1 and treatment period 2 will be listed.

The following summaries will be provided: % based on the total number of FAS patients:

- Number (%) of patients who were randomized (based on data from IRT system)
- Number (%) of patients who were randomized but not treated (based on ‘DAR’ eCRF page not completed for any study treatment component)
- Primary reason for not being treated (based on “End of Treatment Phase Completion” eCRF page)
- Number (%) of patients who were treated (based on ‘DAR’ eCRF pages of each study treatment component completed with non-zero dose administered)
- Number (%) of patients who are still on-treatment (based on the ‘End of Treatment Phase’ page not completed);
- Number (%) of patients who discontinued the study treatment phase (based on the ‘End of Treatment Phase’ page)
- Primary reason for study treatment phase discontinuation (based on the ‘End of Treatment Phase’ page)
- Number (%) of patients who have entered the post-treatment follow-up (based on the ‘End of Treatment Phase’ page);
- Number (%) of patients who have discontinued from the post-treatment follow-up (based on the Study Evaluation Completion/ End of Post-treatment follow-up page);
- Reasons for discontinuation from the post-treatment follow-up (based on Study Evaluation Completion/ End of Post-treatment follow-up page);
- Number (%) of patients who have entered the survival follow-up (based on the ‘End of Treatment Phase’ or ‘End of Post-treatment follow-up’ page).

### **Protocol deviations**

The number (%) of patients in the FAS with any protocol deviation will be tabulated by deviation category (as specified in the study Data Handling Plan) overall and by treatment group for the FAS. Major protocol deviations leading to exclusion from analysis sets will be tabulated separately overall and by treatment group. All protocol deviations will be listed.

### **Analysis sets**

The number (%) of patients in each analysis set will be summarized by treatment group.

## **2.4 Treatments (study treatment, rescue medication, concomitant therapies, compliance)**

The safety set will be used for the analyses below.

The average daily dose, cumulative dose, duration of exposure in treatment period 1 to ruxolitinib or placebo, dose intensity will be listed and summarized by treatment group. Duration of exposure and duration of follow up will be categorized into time intervals; frequency counts and percentages will be presented for the number (%) of subjects in each interval. The number (%) of subjects who have dose reductions or interruptions, and the reasons, will be summarized by treatment group.

The dose administration records for both treatment period 1 and treatment period 2 will be listed, including the duration of exposure for patients who will enter treatment period 2.

Concomitant medications including prohibited medications, and significant non-drug therapies prior to and after the start of the study treatment will be summarized for all patients and by treatment group.

#### **2.4.1 Study treatment / compliance**

**Duration of exposure in treatment period 1** is considered by taking into account the duration of exposure to ruxolitinib or placebo.

Duration of exposure in treatment period 1 (days) = (date of last administration of study treatment in treatment period 1) – (date of first administration of study treatment in treatment period 1) + 1.

**Duration of exposure in treatment period 2** is considered by taking into account the duration of exposure to open label ruxolitinib.

Duration of exposure in treatment period 2 (days) = (date of last administration of study treatment in treatment period 2) – (date of first administration of study treatment in treatment period 2) + 1.

Summary of duration of exposure in treatment period 1 of study treatment in appropriate time units will include categorical summaries and continuous summaries (i.e. mean, standard deviation etc) using appropriate units of time.

**Duration of follow up** is defined as last contact date – randomization date + 1.

The **average daily dose** refers to the actual daily dose administered.

The **cumulative dose in treatment period 1** refers to the total actual dose administered, over the duration exposure in treatment period 1.

**Dose intensity in treatment period 1 (DI1)** for subjects with non-zero duration of exposure in treatment period 1 is defined as follows:

$DI1 \text{ (mg/day)} = \text{Actual Cumulative dose in treatment period 1 (mg)} / \text{Duration of exposure to study treatment in treatment period 1 (days)}$ .

The number of subjects who have dose reductions, permanent discontinuations or interruptions, and the reasons, will be summarized separately for each of the study treatment components.

‘Dose changed’, ‘Dose interrupted’, and ‘Dose permanently discontinued’ fields from the Dosage Administration CRF pages (DAR) will be used to determine the dose reductions, dose interruptions, and permanent discontinuations, respectively.

The corresponding fields ‘Reason for dose change/dose interrupted’ and ‘Reason for permanent discontinuation’ will be used to summarize the reasons.

For the purpose of summarizing interruptions and reasons, in case multiple entries for interruption that are entered on consecutive days with different reasons will be counted as

separate interruptions. However, if the reason is the same in this block of entries, then it will be counted as one interruption.

The protocol allows use of dose tapering strategy for patients who permanently discontinue study treatment and a separate summary will be produced with the number of patients for whom dose tapering will be recorded in treatment period 1 and treatment period 2.

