6.3 Dose modifications

6.3.1 Dose modification and dose delay

6.3.1.1 Dose modification for hematologic toxicity

Treatment Period 1

Dose reductions or interruptions for hematological changes are permitted in order to allow the patient to continue on the study treatment. The maximum allowed doses for different ranges of cytopenia is described in [Table 6-4](#). The objective of the dose adjustment rules is to optimize treatment response for each individual patient while avoiding significant cytopenia. Dosing may be restarted or increased following recovery of the hematologic parameter(s) to acceptable levels. Any patient requiring dose interruption continuously for more than 4 weeks

due to decreases in ANC or platelet (PLT) counts must be permanently discontinued from treatment. Hb levels decreasing below 8g/dL with an absolute drop of 3g/dL from baseline, will constitute a marker of progressive MF disease, if Hb levels fail to recover \geq 8g/dL following treatment interruption for two consecutive weeks. Such patients must permanently discontinue study treatment.

Table 6-4 Dose reductions and interruptions due to hematological changes – Treatment Period 1

Current Hb (g/dL)	Maximum allowable dose
< 8	Interrupt dosing (HOLD)
8 to < 10	Reduce total daily dose to 5 mg BID
Current PLT ($\times 10^9/L$)	
< 50	Interrupt dosing (HOLD)
50 to < 75	Reduce total daily dose to 5 mg BID
Current ANC ($\times 10^9/L$)	
< 0.5	Interrupt dosing (HOLD)
0.5 to < 0.75	Reduce total daily dose to 5 mg BID

All dose changes must be recorded on the Dosage Administration Record CRF.

Patients whose dose has been interrupted for more than 4 weeks for any reason are recommended to be permanently discontinued from study treatment.

Treatment Period 2

Dose reductions and interruptions for ruxolitinib treatment during ‘Treatment Period 2’ can be performed in accordance with the local label requirements. In countries where ruxolitinib is not currently approved, treatment should be discontinued for platelet counts less than $50 \times 10^9/L$ or absolute neutrophil counts less than $0.5 \times 10^9/L$. After recovery of blood counts above these levels, dosing may be re-started at 5 mg twice daily and gradually increased based on careful monitoring of complete blood cell count, including a white blood cell count differential.

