6.3.1.3 Optional dose tapering strategy in the event of study treatment discontinuation

Following interruption or discontinuation of ruxolitinib, symptoms of myelofibrosis may return over a period of approximately one week. There have been cases of patients discontinuing ruxolitinib who sustained more severe events, particularly in the presence of acute intercurrent illness. It has not been established whether abrupt discontinuation of ruxolitinib contributed to these events. Unless abrupt discontinuation is required, gradual tapering of the study treatment dose may be considered, although the utility of the tapering is unproven.

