10.4.1 Variable

The primary endpoint is **progression free survival (PFS-1) in Treatment Period 1**. It is defined as the time from date of randomization until earliest time for one of the following events:

- Progressive splenomegaly as assessed by doubling of spleen volume (by MRI/CT); in addition to an absolute spleen volume of greater than 450 cm³.
- Circulating peripheral blast counts > 10% (requires confirmation after 8 weeks)
- Leukemic transformation defined by an increase in peripheral blood blast percentage to $\geq 20\%$ that is sustained for at least 8 weeks or a bone marrow blast count of $\geq 20\%$
- Hb < 10g/dl with an absolute decrease of at least 3 g/dl from baseline levels (requires confirmation following 2 week of dose interruption/reductions to ensure this is not drug induced cytopenia. In case of Hb stabilizing following dose modification within the 2 weeks, study drug can be re-escalated based on investigators discretion. See section 6.3 for guidance on dosing modifications)
- WBC counts > 25 x 10³/ μ L

- Confirmed MF-7 score of ≥ 30 in addition to an individual symptom score of ≥ 7 in at least one non-splenomegaly related symptom, i.e., tiredness, night sweats, itching (pruritus), bone pain (diffuse not joint pain or arthritis). (Confirmed on two consecutive weeks)
- Death from any cause

As the proposed study intends to investigate the benefit of ruxolitinib in delaying the emergence of MF associated symptoms, MF-7 is expected to objectively evaluate disease progression based on the worsening of symptoms through symptom scores. A clinically relevant threshold of ≥ 30 was set to capture the time point when the patient begins experiencing more symptomatic disease (disease progression) reflected by a minimum of doubling in the baseline MF-7 scores. Additionally, progression by symptom will also require an individual score of ≥ 7 in at least one non-splenomegaly related symptom, i.e., tiredness, night sweats, itching (pruritus), bone pain (diffuse not joint pain or arthritis).

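### SAP 2.4.1 derives dose reductions from a CRF field that does not show direction, and does not exclude taper steps

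*SAP*

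**What the plan says.** SAP 2.4 promises this table: "The number (%) of subjects who have dose reductions or interruptions, and the reasons, will be summarized by treatment group". SAP 2.4.1 supplies the derivation. It lists the fields *Dose changed*, *Dose interrupted* and *Dose permanently discontinued*, and states that these "fields from the Dosage Administration CRF pages (DAR) will be used to determine the dose reductions, dose interruptions, and permanent discontinuations, respectively". The final word of that quote pairs *Dose changed* with reductions. Reasons come from two fields, one shared by dose changes and interruptions and one for permanent discontinuation, which "will be used to summarize the reasons". The same section explains how to count consecutive interruption entries. It has no matching rule for reductions.

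On tapering, SAP 2.4.1 adds that "a separate summary will be produced with the number of patients for whom dose tapering will be recorded in treatment period 1", and likewise for period 2. It does not say that these patients or records leave the reduction table.

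The protocol allows several kinds of dose change:
- Section 6.3.1.1: "Dosing may be restarted or increased following recovery of the hematologic parameter(s) to acceptable levels".
- Section 10.4.1, after a haemoglobin-driven modification: "study drug can be re-escalated based on investigators discretion".
- Section 6.3.1.3, at discontinuation: "gradual tapering of the study treatment dose may be considered".

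Section 6.3.1.1 also requires every dose change to be entered on the dosage administration record (DAR), and section 6.1.1 requires the doses taken to be entered there.

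**The concern.** A dose reduction is normally read as a tolerability result: the patient could not stay on the assigned dose. A field that only says the dose changed cannot tell a reduction from a return to full dose, or from a step in a planned withdrawal of treatment. If the table is programmed as SAP 2.4.1 is written, some subjects who never had their dose lowered for tolerability could be counted. The reason column could also mix recovery and tapering with toxicity.

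Tapering deserves particular attention because the study was stopped early for recruitment reasons (SAP 1). Subjects still on treatment had to come off study treatment for a reason unrelated to tolerability, and the protocol lets such subjects be tapered.

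**Working it through.** The documents give no figure that depends on this rule, so there is nothing to reproduce. The check sets the rule against the dosing patterns that the protocol permits.

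**Inputs**
- Reported statistic: subjects, not entries (SAP 2.4 and 2.4.1).
- Period 1 start: 10 mg BID for every patient (Protocol 6.1.1).
- Planned escalation above the start: none (Protocol 6.2 is marked not applicable).
- Reduction rule: based on *Dose changed*, with no condition on direction (SAP 2.4.1).
- Taper: identifiable, since it has its own summary (SAP 2.4.1).
- Assumption: the reduction table covers Treatment Period 1. SAP 2.4 summarises exposure for that period and lists dosing records for both periods.

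**Is the subject counted as having a reduction?**

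| Pattern in Period 1 | Rule as written | Direction check only | Direction check plus taper exclusion |
|---|---|---|---|
| Full dose, then lower dose | Yes | Yes | Yes |
| Full, lower, back to full | Yes, once | Yes, once | Yes, once |
| Full, hold, lower | Yes, if the restart is recorded as *Dose changed* | Yes | Yes |
| Full, hold, full | Yes, if the restart is recorded as *Dose changed* | No | No |
| Full throughout, then tapered | Yes, if a taper step is recorded as *Dose changed* | Yes | No |

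**Reading the table**
1. In Period 1 everyone starts at the same dose and no escalation above it is planned. An increase can therefore only follow a reduction or an interruption. After a reduction, the subject is already in the numerator, so re-escalation adds no one. It can affect only the tabulated reasons.
2. Two patterns can add a subject wrongly: a full-dose restart after a hold, and a taper in someone with no earlier reduction. Both depend on how the site completes the DAR.
3. Checking direction alone does not settle the taper pattern. A taper step is a genuine move to a lower non-zero dose and passes that check. Only an explicit exclusion removes it.

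**Size**

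Let an arm have n subjects, of whom r have a true reduction. Let k be the subjects without a true reduction whose only *Dose changed* entries are full-dose restarts or taper steps. The reported proportion is (r + k)/n instead of r/n, an excess of k/n, with k between 0 and n − r. Neither k nor the number tapered is given. The DAR form and its completion instructions are not in the documents either, so the excess cannot be narrowed further and may be zero.

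**The case against.** The strongest reply is that SAP 2.4.1 names source fields and does not set out an algorithm. On that view, saying that a field is used to determine reductions leaves room for an obvious check against the recorded doses, and a competent programmer would make it. This is a fair account of what might be done. It does not rescue the text, which pairs one field with one category and states no further condition. It also does not deal with tapers, which pass the direction check.

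Other parts of the reply stand and limit the point:
- A reader might infer that each reduce-then-re-escalate episode counts as two reductions. It does not, because the table counts subjects and no count of reduction events is planned.
- A reader might infer that tapered patients are counted twice, or that the table largely measures the study's termination. The documents do not show this. Tapering is optional, and whether a taper step also sets *Dose changed* depends on a form we do not have. How patients came off treatment is set out in a Premature Termination Plan that we also do not have. Protocol 4.3 foresees efforts to continue treatment outside the study for patients still benefiting, so leaving the study need not mean a taper.
- A reader might infer that little other tolerability information remains. SAP 2.8.1 keeps adverse events by grade and relationship, and those leading to discontinuation or to interruption or adjustment. SAP 2.8.3 keeps laboratory shift tables and boxplots of haemoglobin and platelets. The adverse event tables do not rest on this field mapping.
- Dosing records are listed for both periods (SAP 2.4), and SAP 1.2 calls the number randomised minimal. A misclassified subject could therefore be found by reading the listing.

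**Conclusion.** Wrong as written, and minor. The rule ties reductions to a field without direction, while the protocol permits dose changes that are not reductions for tolerability. Followed literally, it can misclassify subjects whose only changes are taper steps or full-dose restarts, and it can mix the reasons for re-escalations and tapers into the reduction reasons.

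The size is unknown and may be zero. It rests on three things: that such changes are recorded under *Dose changed*, that the programming follows the text, and that the table is limited to Period 1. The documents do not support the stronger statement that re-escalations and taper steps are in fact reported as reductions. No hypothesis is tested in this abbreviated analysis (SAP 2.5), so only descriptive exposure output is affected.

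**What to change.** Replace the reduction part of the field mapping in SAP 2.4.1 with a derivation from recorded doses:
- Count a dose reduction only when a recorded non-zero daily dose is lower than the preceding non-zero daily dose. Comparing non-zero doses handles holds: a restart at the same dose is not a reduction, and a restart at a lower dose is.
- Leave changes to a higher dose, and their reasons, out of the reduction table.
- Exclude records identified as tapering, which already have their own summary.

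The cost is one SAP paragraph and a small programming change. The doses are already on the DAR (Protocol 6.1.1), and the SAP already plans to identify tapered patients, so no new data are needed.

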## **2.4.2 Prior, concomitant and post therapies**

### **Prior MF therapy**

Prior medications to treat MF will be listed and summarized by ATC class, preferred term, overall and by treatment group by means of frequency counts and percentages using FAS.

### **Post treatment anti-cancer therapy**

Anti-neoplastic therapies since discontinuation of study treatment will be listed and summarized by ATC class, preferred term, overall and by treatment group by means of frequency counts and percentages using FAS.

### **Concomitant medications**

Concomitant therapy is defined as all interventions (therapeutic treatments and procedures) other than the study treatment administered to a patient coinciding with the study treatment period. Concomitant therapy include medications (other than study drugs) starting on or after the start date of study treatment or medications starting prior to the start date of study treatment and continuing after the start date of study treatment.

Concomitant medications will be coded using the <World Health Organization (WHO) Drug Reference Listing (DRL) dictionary that employs the WHO Anatomical Therapeutic Chemical (ATC) classification system and summarized by lowest ATC class and preferred term using frequency counts and percentages. Surgical and medical procedures will be coded using MedDRA and summarized by SOC and preferred term. These summaries will include:

1. Medications starting on or after the start of study treatment but no later than 30 days after start of last dose of study treatment and
2. Medications starting prior to start of study treatment and continuing after the start of study treatment.

All concomitant therapies will be listed. Any concomitant therapies starting and ending prior to the start of study treatment or starting more than 30 days after the last date of study treatment will be flagged in the listing. The safety set will be used for all concomitant medication tables and listings.

## **2.5 Analysis of the primary objective**

The study was terminated prematurely with insufficient sample size and study duration to evaluate the effect of ruxolitinib in delaying progression of MF from early disease to more advanced disease stages. Therefore, the initial primary end point, progression free survival

(PFS), will not be derived and no statistical hypothesis will be tested. Consequently, no supportive analysis for per protocol set is planned.

The early terminated study aims to present data collected for the endpoints of interest, including change in spleen volume and length from baseline, change in symptoms using MF-7 and EQ-5D from baseline (see patient reported outcomes section), safety endpoints [REDACTED]. Descriptive statistics will be used to summarize the endpoints of interest and the FAS will be used for analyzing the data. Change in spleen volume and palpable spleen length below costal margin

Regular assessments of spleen volumes via Magnetic Resonance Imaging (MRI) or Computed Tomography (CT) are performed to evaluate progressive splenomegaly. Spleen size is assessed by palpation and measured in centimeters using a soft ruler, from the costal margin to the point of greatest splenic protrusion.

Spleen volume, spleen length, absolute change and percentage change in spleen volume by MRI/CT and palpable spleen length below costal margin will be summarized descriptively by treatment for each assessment timepoints.

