7.2 Assessment types

7.2.1 Efficacy assessments

7.2.1.1 Assessments for primary efficacy endpoint (progression free survival – PFS-1)

The criteria for disease progression (PFS-1) will be assessed for determination of the primary endpoint of progression free survival in accordance with [Section 10.4.1](#). For patients meeting the progressive disease criteria the Investigator must review according to the guidance below, and confirm the relevant criterion. The data should be entered in the appropriate CRF and IRT notified.

Guidance for progressive disease criterion assessment:

- Earliest confirmed single disease progression criterion should be entered.
- If more than one criterion are confirmed on the same date, time or visit (+ 14 days from the date of first confirmed criterion); progressive disease should be assessed using the single criterion based on the hierarchy below:
 1. Death
 2. Leukemic transformation
 3. Splenomegaly
 4. Symptom (MF-7 score)
 5. Hematologic criteria. Note: In the case of more than one hematologic criteria, the investigator should assess the key contributing criterion to declare disease progression

The following assessments will be utilized to assess and confirm disease progression.

1. Spleen volume determination by MRI/CT:

Evaluation of progressive splenomegaly will be performed by regular assessments of spleen volumes via Magnetic Resonance Imaging (MRI) or Computed Tomography (CT) where MRI is contraindicated to ensure an objective and unbiased assessment. MRI (or CT) of the spleen will be performed at screening (within 7 days prior to randomization), every 12 weeks and at the end of treatment ([Table 7-1](#)). An end of treatment MRI (or CT) assessment is only required for patients who discontinue treatment due to disease progression if a MRI (or CT) scan was not performed within 6 weeks of study treatment discontinuation. Patients who enter the post treatment follow up phase after study treatment discontinuation for reasons other than disease progression should have their assessments performed as per the visit schedule at the time of discontinuation.

A designated central imaging laboratory will be used to collect all imaging data; perform quality check and provide read-out for the study. The scans from an individual patient will be read by a central reader upon transfer from the site radiologist. Results from the central evaluations will be used for primary analyses.

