laboratory test, or other assessments. As far as possible, each adverse event should be evaluated to determine:

1. The severity grade (CTCAE Grade 1-4)
2. Its duration (Start and end dates) (add or Ongoing at End of Study for NOVDD)
3. Its relationship to the study treatment (Reasonable possibility that AE is related: No, Yes)
4. Action taken with respect to study or investigational treatment (none, dose adjusted, temporarily interrupted, permanently discontinued, unknown, not applicable)
5. Whether medication or therapy was given (no concomitant medication/non-drug therapy, concomitant medication/non-drug therapy)
6. Outcome (not recovered/not resolved, recovered/resolved, recovering/resolving, recovered/resolved with sequelae, fatal, unknown) Delete for NOVDD Trials as outcome is not collected
7. Whether it is serious, where a serious adverse event (SAE) is defined as in Section 8.2.1.

All adverse events should be treated appropriately. If a concomitant medication or non-drug therapy is given, this action should be recorded on the Adverse Event CRF.

Once an adverse event is detected, it should be followed until its resolution or until it is judged to be permanent, and assessment should be made at each visit (or more frequently, if necessary) of any changes in severity, the suspected relationship to the study treatment, the interventions required to treat it, and the outcome.

[figure not shown]
Confirmation of progression of disease, based on criteria described in [Section 10.4.1](#) should not be reported as adverse event. However death should be reported as SAE ([Section 8.2](#)).

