10.4.4 Supportive analyses

A summary of first progression (PFS-1) events will be tabulated by treatment group.

A subgroup analysis of PFS will be performed by IPSS risk group, type & number of HMR mutations, presence of palpable splenomegaly and/or active symptoms as determined by MF-7.

The analysis of PFS will be repeated for per protocol set.

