**Document History – Changes compared to previous final version of SAP**

Date	Time point	Reason for update	Outcome for update	Section and title impacted (Current)
29-Jan-2016	Prior to DB lock	Creation of final version	N/A - First version	NA
19-Jul-2017	Prior to DB lock	Creation of amendment 1 due to study premature termination	Change to the ultimate goal of the early termination study: To present the efficacy, safety and [REDACTED] data of interest.	Introduction section 1.2
			Specified that primary endpoint PFS, and other time to event endpoints will not be derived.	Introduction section 1.2
			Removed Per-Protocol Set and PK Set, and Subgroup of interest.	Analysis sets Section 2.2
			Treatment period 1 data will be tabulated, Treatment period 1 and period 2 data will be listed.	Sections 2.3, 2.4, 2.5, 2.7, 2.8
			Specified that no analysis for primary endpoint is planned. The early terminated study aims to present data collected for the endpoints of interest, including change in spleen volume and length from baseline, change in symptoms using MF-7 and EQ-5D from baseline (see patient reported outcomes section), safety endpoints, [REDACTED]	Analysis of the primary objective section 2.5
			Descriptive statistics will be used to summarize the endpoints of interest and the FAS will be used for analyzing the data.	
			Specified that no sufficient data were collected to assess the effect of ruxolitinib versus placebo on overall survival and time to progression, so that no secondary	Analysis of the secondary objectives section 2.7

Date	Time point	Reason for update	Outcome for update	Section and title impacted (Current)
			efficacy analysis will be performed in this study.	
			AESI is not planned for this prematurely terminated study.	Section 2.8.1.1
			Add text to AE of clinical trial safety disclosure.	Section 2.8.1.2
			No formal PK analysis is planned. Individual plasma ruxolitinib concentration data will only be listed for the Full analysis set.	PK Section 2.9
				

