### 1.2 Study objectives and endpoints

Table 3-1 of CINC424A2353 study protocol specifies the study objectives and endpoints. The initial plan of efficacy evaluation and safety assessment of ruxolitinib cannot be implemented due to early termination of the study. The number of patients randomized and the study duration by termination were minimal and they did not provide sufficient information to perform formal comparison specified in the original analysis plan.

To present the efficacy, safety and [REDACTED] data of interest is the ultimate goal of the early termination study. The key endpoints of interest are listed in Table 1-1 below.

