## 4 Change to protocol specified analyses

Not applicable.

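### After early termination, does the SAP still need a by-arm count of PFS-1 events by criterion?

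*SAP*

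**What the plan says.** Protocol 10.4.4 plans, as support for the primary analysis: "A summary of first progression (PFS-1) events will be tabulated by treatment group". It does not ask for a breakdown by criterion. Protocol 7.2.1.1 has the investigator confirm progression and record it in the CRF: "Earliest confirmed single disease progression criterion should be entered".

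SAP amendment 1 was written after the study was terminated for recruitment reasons. Section 2.5 states that PFS "will not be derived and no statistical hypothesis will be tested". It names the per-protocol analysis as dropped and is silent on the event summary. Section 2.7 drops secondary efficacy analysis. Section 1.2 gives the reason: "The number of patients randomized and the study duration by termination were minimal". The Document History table records the change: "Specified that primary endpoint PFS, and other time to event endpoints will not be derived".

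The SAP keeps a Treatment Period 1 disposition table (Section 2.3.1), with the numbers who "permanently discontinued from treatment period 1 and went to treatment period 2" and the primary reason for discontinuation. Section 4, headed "Change to protocol specified analyses", is marked as not applicable.

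**The concern.** A log-rank test and a hazard ratio need events, but a descriptive count does not. It needs no PFS time and no power, and the SAP still describes spleen volume, symptoms and safety in the same few patients. Dropping the count of primary events, without mention, seems to go further than the stated reason supports.

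The retained summaries do not obviously replace it. Spleen volume is summarized by timepoint and MF-7 as percent change by visit. The PFS-1 definition in Protocol 10.4.1 joins conditions within a patient: spleen doubling together with a volume above 450 cm³, or a confirmed MF-7 score of at least 30 together with an item score of at least 7. Under Protocol 8.1.1 confirmed progression "should not be reported as adverse event", so the adverse event tables will not show it. At stake is whether a reader of the abbreviated report can see how many patients met the primary endpoint, by which criterion and in which arm.

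Section 4 adds to the impression of an incomplete record. It reports no change from the protocol's analyses, and three protocol safety tables are missing from the visible SAP without appearing in the history table.

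**Working it through.** **1. Scale of the original design.** Inputs from Protocol 10.8: hazard ratio 0.50, one-sided 2.5%, 90% power, 1:1 allocation, 90 events.
- Events (Schoenfeld) = 4(1.960 + 1.282)² / (ln 2)² = 42.03 / 0.4805 = 87.5, rounded up to 88. This agrees with the stated 90.
- Power at 90 events = Φ(½√90 × ln 2 − 1.960) = Φ(1.328) = 90.8%.

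**2. Events likely at termination.** The documents do not give the number randomized. Assumption: *n* = 3 to 20 per arm, all followed for *m* = 3 to 12 months, no dropout, exponential PFS with the planning medians of 50 and 100 months.
- Expected events = n(1 − exp(−m ln 2/50)) on placebo and n(1 − exp(−m ln 2/100)) on ruxolitinib.
- P(at least one) = 1 − exp(−nm(ln 2/50 + ln 2/100)).

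| n per arm | months | placebo | ruxolitinib | total | P(≥1 event) |
|---|---|---|---|---|---|
| 3 | 3 | 0.12 | 0.06 | 0.18 | 17% |
| 5 | 4 | 0.27 | 0.14 | 0.41 | 34% |
| 20 | 12 | 3.07 | 1.60 | 4.66 | 99% |

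Even 5 events would give power of about Φ(½√5 × ln 2 − 1.960) = Φ(−1.185) = 12%. Dropping inference is plainly right.

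**3. Could a bare count inform the planning rate?** The planned placebo rate is ln 2/50 = 0.0139 per month. With zero events the exact 95% upper limit is 3.689/person-months. It falls below that rate only beyond 3.689/0.01386 = 266 placebo person-months, and the assumed range reaches at most 20 × 12 = 240. An excess could contradict the rate: 8 events in 240 person-months have an exact lower limit of 0.0144. That would be well above the 3.07 expected, so it is possible but not likely if the planning rate is right.

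**4. Where each PFS-1 event would appear in the retained outputs.**

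| Criterion (Protocol 10.4.1) | Retained output (SAP) |
|---|---|
| Spleen doubling and > 450 cm³ | Volume and percent change by timepoint (2.5); assessments listed (2.1.10); Period 2 entry (2.3.1) |
| MF-7 ≥ 30 with an item ≥ 7 | Percent change in total and items by visit (2.11); Period 2 entry (2.3.1); patient listing only under the general rule in 2.1.10 |
| Hemoglobin, WBC | Listed by test, patient and study day (2.8.3) |
| Leukemic transformation | Marrow blast percentage listed (2.13) |
| Peripheral blasts > 10% | Discontinuation reason (2.3.1); blasts are not named in the hematology panel of Protocol Table 7-2 |
| Death | Tabulated and listed (2.8.1, 2.8.2) |

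**5. Completeness.** Protocol 7.1.5 requires study treatment to stop at progression in Period 1 unless the patient enters Period 2. Each confirmed on-treatment progression therefore falls under one of two entries tabulated in SAP 2.3.1. Progression after stopping for another reason ends post-treatment follow-up (Protocol 7.1.7.2), and reasons for leaving that phase are tabulated too. Protocol 10.4.3 would have censored those events in the primary analysis anyway.

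**6. The safety tables.**
- The frequency table of newly occurring grade 3 or 4 laboratory values is missing, but SAP 2.8.3 keeps baseline-to-worst shift tables and a separate listing of those values.
- The ECG shift table is replaced by a listing (2.8.4.1).
- The vital-signs shift table is replaced by change-from-baseline statistics and flagged notable values (2.8.4.2).

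**The case for a change.** The best case for a change is that the table would be cheap and the investigator's criterion is already in the CRF. Rebuilding events from listings is not the same as reporting the primary endpoint, and even a stated zero tells the reader something. Section 2.5 names the per-protocol analysis as dropped but lets the event summary lapse in silence.

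Part of this stands. No single visible output gives the qualifying criterion by arm. The MF-7 and peripheral-blast criteria are the hardest to rebuild. Section 4 is wrong on its face.

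The rest is weaker. The Protocol 10.4.4 summary supported a PFS analysis that is no longer done, so its lapse is consistent with Section 2.5. A count by criterion would be a new output, since the protocol never specified that split. It would also be less simple than it looks. Protocol 7.2.1.1 has the investigator enter the criterion yet uses central evaluations for the primary analyses. The table would need a rule on that, and another on events that Protocol 10.4.3 censors. The documents do not show that confirmation dates or unconfirmed events are CRF fields. Parts of the SAP are redacted, so the absence of such an output cannot be stated with certainty.

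**Conclusion.** No change is needed. The gap is one of convenience. Total progressions should be visible through discontinuation reason and Period 2 entry, deaths are reported, and most criterion-level facts can be read patient by patient in a study the SAP itself calls minimal. Under the assumed range the missing table would hold about 0.2 to 4.7 expected events, with no test or interval attached. It would alter no estimate or conclusion, because the SAP openly draws none about PFS.

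The Section 4 entry is clerical: the history table and Sections 1, 1.2, 2.5 and 2.7 already disclose the main departures. The three absent safety tables are not disclosed there, but their content is largely covered by retained shift tables, summaries and listings.

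This rests on two assumptions: that the end-of-treatment page offers progression as a reason, which the documents do not show but Protocol 7.1.5 makes the natural reading, and that enrolment was indeed very small. With a much larger number of patients and events, a by-criterion table would be worth having.
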